4.6 Rescue medication administration (if applicable)

4.7 Subject Completion/ Withdrawal procedures

- Participants can voluntarily withdraw anytime during the study if they feel that they cannot continue to consume the drinks. They will be paid according to completion of phases of the study.

4.8 Screen failure procedures

-

5 STUDY EVALUATIONS AND MEASUREMENTS (how measurements will be made)

- At baseline and end of week 3, we will measure body weight, body composition, blood pressure, waist circumference, liver fat by transient elastography, MRI scan and serum and urinary biomarkers. Blood and urinary biomarkers will also be measured at one and 3 hour timepoints during the acute fructose challenge.
- Body weight and composition (Body weight, body fat, etc) will be measured through a body fat analyzer (Tanita Corporation of America Inc. Arlington Heights, IL)
- Waist circumference (WC) will be measured using a stretch-resistance tape at the midpoint between the lower margin of the least rib and the top of the iliac crest to the nearest 0.1 inch. Waist and hip circumferences will be measured to the nearest cm in a standing position
- Sitting blood pressure and pulse rate will be measured using the Omron digital blood pressure monitor (HEM907XL, Omron Healthcare Inc. Lake Forest, IL)

- Liver fat will be measured using MRI at the Wakeforest Imaging Center and transient elastography (Fibroscan, Echosens, Paris, FR)

Quality control: All phenotypes will be checked for distribution and accuracy of values. Phenotype data collection will be performed on the same equipment with strict quality control regulations. Assay quality is assessed by tracking coefficients of variation for quality control samples that are run with each assay. Appropriate internal standards will be used wherever necessary.

- 5.1 Efficacy Evaluation (if applicable)**
- 5.2 Pharmacokinetic Evaluation (if applicable)**
- 5.3 Safety Evaluations**

6 STATISTICAL CONSIDERATION

6.1 Primary Endpoint

Our main outcome measure is liver fat estimation through MRI scans, transient elastography (Fibroscan) and fatty liver index.

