	(2) Intervention: This part is divided into two phases. Each phase entails two visits. Phase2-visit 1: The 48 enrolled (24 in each of the high and low genetic risk group) will

visit the UNC NRI clinical suite run by the Human Research Core. They will be taken to the WakeForest imaging center for their baseline MRS scan.

Visit 2: Acute fructose challenge: The next day, they will have their initial anthropometrics and Fibroscan measurements. They will then undergo an oral fructose challenge using a protocol used by Hudgins et al¹³. The participants will be provided with a drink consisting of fructose (0.75g/kg body weight) + glucose (0.45g/kg body weight) dissolved in 24 Oz of water (equal to 2 soda cans) to be consumed within 15 minutes. Blood and urine will be sampled at baseline and 1 and 3 hours after sugar drink ingestion. During the challenge period, no other beverage (except water) or food will be allowed.

3-week intervention: The 48 participants will be provided with sugar drinks for the three week period. The drinks that need to be taken per day will contain fructose (0.75g/kg body weight) + glucose (0.45g/kg body weight) dissolved in 24 Oz of water (equal to 2 soda cans) which is similar to that provided during the acute fructose challenge⁷.

[figure not shown]
Addition of glucose to fructose in the challenge and 3-week intervention induces the lipogenic effects of fructose, alleviates gastrointestinal effects of fructose and mimics the real-life situation¹⁴. They will visit at the end of each week to collect drinks for the next week. In addition, participants will be given standardized meals for the day prior to the baseline fructose challenge. They will also be instructed to avoid alcohol, juices and sodas the previous evening.

Efficacy Evaluations	Changes in liver fat accumulation through MRI scans and fibroscan measurements, and serum concentration of other lipids, liver function markers and uric acid.
Pharmacokinetic Evaluations	N/A

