Safety Evaluations	
At screening, to check for blood glucose values, we will conduct a spot glucose check using a glucometer (Accu-Chek, Roche Diagnostics, CH) to check that the glucose levels of the participants are in the normal range (fasting < 100mg/dl, post meal < 140 mg/dl and random < 200 mg/dl). Secondly, we will have a physician who will be available if needed. We will also conduct pregnancy test if needed.
 
Also, we will exclude participants for further participation if we find that the participant has high liver fat fraction (>5%) during our baseline MRI scan¹⁰. The participant will be given a report that they can show to their physician for treatment.

Statistical And Analytic Plan	Our main outcome measure is change in liver fat via MRI scan, fatty liver index equation and through fibroscan measurements. We will also measure serum concentrations of other lipids, liver function markers and uric acid. Data will be assessed using descriptive measures and confidence intervals. Paired t-tests and repeated measures regression analysis will be performed to explore the significant differences between week 0 and week 3.
DATA AND SAFETY MONITORING PLAN	A data and safety monitoring plan will be instituted for this study that will ensure adherence to the protocol approved by UNC IRB. [name] (PI) and co-investigators will review the phenotype and genotype data as they are generated. Any adverse event that is reported to either the principal investigator or her designated research associates by the subject or medical staff caring for the subject and which meets the criteria will be documented as such. Any event that is reported will then generate an adverse event report, which will be submitted to the IRB. The report will include a description of the event, when and how it was reported, as well as any official chart records or documentation to corroborate the event or the reporting of the event

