Genes and gene by nutrient interactions play a major role in the regulation of NAFLD: Both genetic and environmental factors contribute to the onset and progression of NAFLD. NAFLD is a complex and heritable phenotype. Family-based studies have reported heritability estimates for NAFLD to be between 20% and 70%^{7,8}. Genome-wide and candidate gene studies have identified several genes associated with NAFLD⁸. Representative genes that were implicated in lipid metabolism and in the development and progression of NAFLD are shown in **Table1**. Few studies have shown that fructose affects lipogenesis in liver in a genotype-specific manner. Davis and colleagues found that Hispanic children with GG genotypes of *PNPLA3* SNP rs738409 were more inclined to accumulate fat in the liver as compared to children with CC or CG genotypes³. Similarly, another study investigating the effects of added sugars on liver fat found that individuals with TT of rs1260326 of *GCKR* increased their *de novo* lipogenesis by 44% during an oral fructose + glucose challenge⁴. However, none of the studies have shown the cumulative effects of SNPs on change in liver fat when exposed to fructose.

The genetic-specific effects of fructose on liver lipogenesis need to be studied as a first step towards individualized nutrition: This study assumes significance given that fructose affects liver lipogenesis differentially based on genotypes. It also paves the way towards individualized or personalized nutrition. Previous studies investigating the metabolic effects of fructose have been controversial. Some have shown significant effects of fructose on insulin sensitivity and *de novo* lipogenesis and triglycerides while others have shown no effects²³⁻²⁷. The range of these studies is wide, with the duration of the intervention ranging from 7 to 665 days, sample size ranging between 8 and 64 per group and amount of fructose per day ranging from 40 to 250g/d. For this exploratory and feasibility study we have selected the duration of 21 days, sample size as 12 per group and amount of fructose a ~0.75g/kg/day (equivalent to two sodas/per day).

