2 STUDY OBJECTIVE

2.1 Our goal for this study is to generate preliminary data that is needed to support an application to NIH for funding of a larger, adequately-powered study to explore whether a set of genotypes, that increase the risk for nonalcoholic fatty liver disease (NAFLD), predispose individuals to increased *de novo* lipogenesis (DNL) and liver fat accumulation when exposed to fructose intake.

2.2 Primary Objective: To explore the genetic-specific effects of fructose on liver fat accumulation using MRI

2.3 Secondary Objective: To explore the genetic-specific effects of fructose on markers of liver fat accumulation (fibroscan⁵ and fatty liver index⁶) and serum biomarkers related to lipids, uric acid and liver function.

3 INVESTIGATIONAL PLAN (brief overview)

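### Sections 6.1 to 6.3 do not carry over the plan's own hierarchy (MRI first) or its between-group comparison, and the acute and DNL aims have no designated measure in the available text

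*Combined protocol and SAP*

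**What the plan says.** **Objectives.** Section 2.2 has "Primary Objective: To explore the genetic-specific effects of fructose on liver fat accumulation using MRI". Section 2.3 has "Secondary Objective: To explore the genetic-specific effects of fructose on markers of liver fat accumulation", and gives Fibroscan and FLI as those markers. The synopsis objectives rank the measures the same way. The synopsis primary objective also covers an acute as well as a longer fructose effect, both by MRI.

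**Endpoints.** Section 6.1 has "Our main outcome measure is liver fat estimation through MRI scans, transient elastography (Fibroscan) and fatty liver index". The synopsis Statistical And Analytic Plan has "Our main outcome measure is change in liver fat via MRI scan, fatty liver index equation and through fibroscan measurements". Section 6.2 lists serum biomarkers only.

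**Analysis.** For liver fat, Section 6.3 and the synopsis statistical plan name paired t-tests and repeated measures regression for week 0 against week 3. Section 6.3 adds a linear regression on an AUC from the acute challenge. Item c of the synopsis Study Design, which belongs to Aim 1, names both a paired and an unpaired t-test, the latter between the two risk groups.

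**Acute and DNL aims.** Aim 2 concerns the acute effect on hepatic DNL and lists Fibroscan as its measure. Aim 3 refers to DNL markers and lists serum liver function markers, lipids and uric acid.

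**Group size.** The synopsis has "48 enrolled (24 in each of the high and low genetic risk group".

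**The concern.** Section 6 is what an analyst would follow. Read alone, it leads to a change over time on three measures of equal standing. The objectives ask for something else: whether the change in MRI liver fat differs between high- and low-risk participants.

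Two things are at stake. First, with three unranked main outcomes, Section 6 does not stop Fibroscan or FLI from leading the report once the results are known. FLI is the weakest substitute. Section 4.2 itself calls it a surrogate, and two of its four inputs (triglycerides and GGT) also belong to the secondary serum endpoints, so it can move with triglycerides while liver fat stays the same. Second, Section 6.4 says the data will be used to size larger studies of gene-nutrient interaction. Those need the between-group difference in change, and its SD, on one named measure.

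Separately, the acute part of the synopsis primary objective and the DNL part of Aims 2 and 3 ask for effects that the listed measures do not capture.

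**Working it through.** The plan gives no alpha, effect size, SD or power, so it has no figure of its own to reproduce. The check is mainly a comparison of sections.

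**1. Endpoint hierarchy**

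| Place | MRI | Fibroscan | FLI |
|---|---|---|---|
| Primary objective (synopsis, 2.2) | primary | not named | not named |
| Secondary objective (synopsis, 2.3) | not named | secondary | secondary |
| Section 6.1 | main | main | main |
| Synopsis statistical plan | main | main | main |
| Section 6.2 | not listed | not listed | not listed |

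Fibroscan and FLI are secondary in the objectives and main outcomes in the endpoint section. They are absent from the section where the objectives would put them.

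For illustration only, assume three unadjusted tests at a two-sided alpha of 0.05 (not in the plan). The chance of at least one false positive is 1 − 0.95³ = 14.3% if they are independent. By simulation it is about 12.5% at correlation 0.5 and 8.3% at 0.9. A single MRI endpoint gives 5%.

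**2. Comparison named for liver fat**

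| Place | Week 0 v week 3 | High v low risk |
|---|---|---|
| Synopsis Study Design, Aim 1 item c | paired t-test | unpaired t-test |
| Synopsis statistical plan | paired t-test, repeated measures regression | not named |
| Section 6.3 | paired t-test, repeated measures regression | not named |

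A repeated measures regression could hold a group-by-time term, but none is stated.

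**3. Precision of the comparison the objective needs**

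Inputs: 24 per risk group (synopsis, Intervention). Assumptions: complete data, and equal SD of change in both groups. The SD is not given, so the result is in SD units.

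Half-width of the 95% CI = t(0.975, 46) × √(1/24 + 1/24) = 2.013 × 0.2887 = 0.58 SD of change.

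**4. Acute effect and DNL**

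- By Section 3.3, the week-0 MRI is on the day before the challenge and the other MRI is at the end of week 3. No pair of scans brackets a challenge, so the difference between them cannot isolate an acute effect.
- By Section 4.2, Fibroscan at the challenge visit comes before the drink. It is the only measure listed under Aim 2, and it measures liver fat and stiffness.
- The assays under Biochemical phenotyping in Section 4.2 are ALT, AST, GGT, uric acid and lipids. None is designated as a DNL marker.
- Blood and urine are planned at baseline, 1 and 3 hours. Section 6.3 names no analyte for the AUC.

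**The case against.** The strongest reply is that the hierarchy and the comparison both exist already. The objectives rank MRI first in two places, so promoting another measure would contradict them. The unpaired t-test is in Aim 1 of the same combined document. The study is declared exploratory and possibly underpowered, no confirmatory decision rests on Section 6.1, and the planned descriptive statistics could supply an SD of change. All of this stands, and it limits the fault to sections that disagree. It does not remove it, because Section 6 is where the endpoint and analysis are fixed.

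Several stronger readings are tempting, and the documents do not support them:

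- *The protocol has no between-group comparison.* It has one, in Aim 1; Section 6.3 does not carry it over.
- *Efficacy Evaluations in the synopsis is a rival primary endpoint.* It reads "Changes in liver fat accumulation through MRI scans and fibroscan measurements, and serum concentration of other lipids, liver function markers and uric acid". That is a list of evaluations and ranks nothing.
- *The comparison rests on 12 per group.* Section 1 does say "sample size as 12 per group", which would give t(0.975, 22) × √(2/12) = 0.85 SD. But the synopsis sets 12 children and 12 young adults in each risk group, hence 24.
- *The wording of Section 6.3 doubles the interval.* The paired half-width in all 48 is t(0.975, 47)/√48 = 0.29 SD, half of 0.58. That ratio holds for any design of this shape and says nothing about the wording.
- *The overall goal promises a DNL outcome from this study.* The sentence ending "lipogenesis (DNL) and liver fat accumulation when exposed to fructose intake" describes what the later, larger study would explore.
- *DNL cannot be assessed at all.* The challenge and the AUC cite a published protocol that is not available here and may specify analytes. The point holds only for the available text.

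**Conclusion.** The concern holds as an inconsistency within the plan that should be fixed. Section 6.1 and the synopsis statistical plan contradict the primary and secondary objectives on which measure leads; this is clear on the text. Section 6.3 omits the high- versus low-risk comparison of liver fat that the objective and the later sample-size work need. At 24 per group that comparison carries a 95% half-width of 0.58 SD of change, given complete data and equal SDs.

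The acute effect by MRI is not observable from the scans described. The DNL part carries less certainty, because it depends on a source that cannot be seen: in the available text no DNL marker and no AUC analyte is named. All three liver measures would still be collected, so the fault is one of pre-specification and no data are lost.

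**What to change.** **Section 6.1 and the synopsis statistical plan.** State one primary endpoint: *change in MRI liver fat (week 3 minus week 0), compared between the high- and low-genetic-risk groups and reported with a 95% confidence interval.*

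**Section 6.2.** Add Fibroscan and FLI.

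**Section 6.3.** Name the unpaired t-test of Aim 1 for the primary endpoint, or its regression equivalent (change on risk group) if the medication covariates of Section 4.5 are used. Keep the paired week 0 versus week 3 analyses as supporting.

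**Acute challenge.** Remove the acute effect from the MRI primary objective in the synopsis. Analyse the challenge as a secondary 0 to 3 hour biomarker AUC, with analytes named from samples already planned (for example triglycerides and uric acid).

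**DNL.** Either designate a DNL measure from what is collected, or reword Aims 2 and 3 and state that the DNL part of the hypothesis in the Study Rationale is not directly tested. Leave the overall goal sentence as it is.

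**Cost.** Wording only, with no new measurements. Fibroscan and FLI lose main-outcome status, and without a designated measure the study cannot claim to assess DNL directly.

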6.2 Secondary Endpoint

Other serum biomarkers such as liver function markers, lipids and uric acid

6.3 Statistical Methods

Each subject will be given sugar drink containing fructose and liver MRI scan with fibroscan measurements will be taken at baseline and end of 3 weeks. Data will be assessed using descriptive measures and confidence intervals. Paired t-tests and repeated measures regression analysis will be performed to explore the significant differences between week 0 and week 3. Also, for each subject, the area under the curve (AUC)¹³ will be computed and a linear regression with AUC as the response will be performed during the acute challenge.

6.4 Sample Size and Power

Although our sample of 48 may not have the power to detect significant effects of fructose on liver fat, this group of 48 well-characterized individuals, focusing only on one ethnicity and one body weight group and specific genotypes will reduce variability and will generate meaningful data. We expect to apply these approaches and use these data to estimate sample size for larger studies with significant power to detect the effects of gene-nutrients interactions on NAFLD and other metabolic disorders.

6.5 Interim Analysis

N/A

7 STUDY INTERVENTION (drug, device or other intervention details)

- Phase 2 &3- visit 2: Acute fructose challenge – each participant will be given a drink made of 24 oz water and fructose (0.75g/kg) and glucose (0.45g/kg).
- 3-week intervention study- each participant will be given a drink to be taken one daily for three weeks starting the next day after acute challenge. These sugar drinks contain the same amount of sugars that are provided as part of the acute fructose challenge

8 STUDY INTERVENTION ADMINISTRATION(if applicable)

N/A

9 SAFETY MANAGEMENT

Data and Safety monitoring plan will be instituted for the project. As per the plan, PI, co-investigators and physician will ensure that the proper protocol is being followed. Any adverse event that is reported to either the principal investigator or her designated research associates by the subject or medical staff caring for the subject and which meets the criteria will be documented as such. Any event that is reported will then generate an adverse event report, which will be submitted to the IRB. The report will include a description of the event, when and how it was reported, as well as any official chart records or documentation to corroborate the event or the

reporting of the event. All adverse events will be graded on a scale from 0 to 5. Any severe and/or unanticipated adverse event will be immediately reported to the safety officer and IRB. All other adverse events will be reported in a timely fashion to IRB, preferably within 2 weeks of the date of the event. All adverse events will be summarized annually and submitted to the IRB. The annual report will address: (1) whether adverse event rates are consistent with pre-study assumptions; (2) reason for dropouts from the study; (3) whether all participants met entry criteria; (4) whether continuation of the study is justified on the basis that additional data are needed to accomplish the stated aims of the study; and (5) conditions whereby the study might be terminated prematurely.

10 DATA COLLECTION AND MANAGEMENT

All personnel with access to data collected for the study are required to sign a Confidentiality Pledge form which states that they understand the sensitive and confidential nature of the data and that divulgence of any information will result in disciplinary action. The pledge is co-signed and kept by the PI. Only authorized staff members have the key to the office and access to the data forms. Passwords and/or encryption keys will be known only to authorized personnel safeguard data on computers at UNC-NRI.

Any adverse event that is reported to either the principal investigator or her designated research associates by the subject or medical staff caring for the subject and which meets the criteria will be documented as such. Any event that is reported will then generate an adverse event report, which will be submitted to the IRB. The report will include a description of the event, when and how it was reported, as well as any official chart records or documentation to corroborate the event or the reporting of the event

11 RECRUITMENT STRATEGY

- Subjects will be recruited through our website <https://www.uncnri.or/index.php/volunteer/> and other community announcements and events

12 CONSENT PROCESS

- All participants will provide informed consent. Each participant will be consented in private. The PI and/or other project investigators will explain the study to the participant and answer questions that the participant might have. If the participant agrees to participate after reviewing the risks/benefits, they will be asked to sign the consent form. For participants who are not adults, their parents permission will also be obtained. We will try our best to explain in a lay person's language so that the participant is completely aware of the risks associated with participation.

13 PLANS FOR PUBLICATION

- We do plan to publish at least one manuscript based on the results of this study.

